#### **Clinical Chart Review**

Additional Clinical Information including: age, gender, demographic data, medical history, cause of brain injury, GCS score (initial, admission, and lowest post-resuscitation), Abbreviated Injury Score (AIS), pupillary reaction at admission, presence of associated injuries, laboratory (BUN, creatinine, alcohol and drug screening) and radiographic data, number of days after insult, length of patient's unconsciousness, length of post-traumatic amnesia (PTA), evidence of hypoxia, duration of ventilatory support, time to follow commands, medication regimen, and duration of stay in the ICU will be recorded from the patients' chart.

#### **Neurological Assessment**

Neurological assessment will consist of a standardized examination of neurologic function as listed in Table 2 by a neurologist or intensivist on the day of admission and the day of the MRS/MRI study.

**Table 2: Neurologic examination**

1. GCS score (initial, admission, post-resuscitation)	7. Motor tone and strength
2. Abbreviated Injury Score (AIS)	8. Deep tendon reflexes
3. Length of unconsciousness	9. Sensory function (touch, pain, temperature)
4. Duration of PTA	10. Cerebellar and basal ganglia function and gait
5. Time until able to follow commands	11. GOS score
6. Cranial nerve examination	12. Length of stay in ICU

### **Enrollment**

Subjects with severe brain trauma will be recruited from admissions to the medical, surgical, or neurological services of LLUMC, which is a Level 1 Trauma Center verified by the American College of Surgeons.

#### TBI Patient enrollment

Only patients that are hemodynamically stable will be targeted for enrollment and the MRS/MRI studies will be ordered only after scheduled repairs for traumatic injuries have taken place. TBI participants will undergo the studies depending on clinical status as determined by the intensivist, [name], attending neurosurgeon or neurologist. Sedation and mechanical ventilation will be continued and monitored for all patients during transport and during the studies by Critical Care nursing and respiratory therapy staff according to hospital policies. Once a potential candidate has been identified, [name] will interview the candidate and/or family members, screen for inclusion/exclusion criteria, and enroll the candidate by obtaining the properly signed consent. The specific inclusion and exclusion criteria are:

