### **Study Objectives**

The goals of this inter-departmental study are: 1) the clinical application of in vivo  $^{13}\text{C}$  MRS at 3T to identify specific metabolic alterations following TBI and 2) determine if changes in cerebral perfusion effect metabolism by limiting metabolic substrate flow into the brain following TBI.

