### **Hypothesis**

We hypothesize that following TBI, metabolic pathways are altered causing an incomplete oxidative of glucose in neurons and astrocytes resulting in a decrease in cerebral metabolism.

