### **Research Design and Methods**

#### Imaging Protocol Overview

All control and TBI subjects will undergo an identical MRS/MRI protocol and neurological exam. MRS/MRI will be performed on a 3T Siemens TIM Trio system equipped with a second radiofrequency channel (Siemens Medical Solutions, Erlangen, Germany) using a specially designed and manufactured  $^1\text{H}$ - $^{13}\text{C}$  dual tuned volume head coil (Advanced Imaging Research, Cleveland,

OH). Sagittal 3D T2 weighted (T2WI) and 3D T1 weighted (T1WI) MR images, reformatted in axial and coronal planes, will be obtained for image co-registration and segmentation. The 2D DSC-PWI sequence will be used to determine cerebral blood flow (CBF), cerebral blood volume (CBV), mean transit time (MTT), and the cerebral metabolic rate of oxygen (CMRO2). Detailed sequence description and image processing methods are explained below.

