#### *TBI Patient Exclusion Criteria:*

- History of neurosurgical intervention, excluding the placement of ventriculostomy shunt
- History of a prior known brain injury with associated loss of consciousness.
- History of a known neurological disorder prior to qualifying injury.
- History of psychiatric disorder.
- History of diabetes or current unstable serum glucose level.
- Renal insufficiency or known history of kidney disease.
- Known contraindication to MRI such as, pacemaker, pregnancy, and/or other non-MR compatible implanted device.

Ten (10) severe TBI patients will have the MRS/MRI study between 3 and 7 days post-injury to target the hypometabolic period.

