#### Control Subject enrollment

Five (5) age/sex matched normal volunteers will be recruited as control subjects during the first year of the study. Control subjects will be recruited from Loma Linda University and/or Medical Center

staff, student or Resident populations. The specific inclusion and exclusion criteria for the control subjects are:

*Control Subject Inclusion Criteria:*

- At least 18 years of age without gender or ethnic restrictions.
- Eligibility for MRI per routine screening checklist.

*Control Subject Exclusion Criteria:*

- MRI Department staff or subordinate of project Investigator.
- History of neurosurgical intervention, excluding the placement of ventriculostomy shunt.
- History of a prior known brain injury with associated loss of consciousness.
- History of a known neurological disorder.
- History of psychiatric disorder.
- History of diabetes or current unstable serum glucose level.
- Renal insufficiency or known history of kidney disease.
- Previous allergic reaction to gadolinium MR contrast.
- Known contraindication to MRI such as, pacemaker, pregnancy, and/or other non-MR compatible implanted device.

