## **Statistical Analysis**

The data analysis will emphasize descriptive and graphical statistics. Descriptive statistics used to detect statistically significant differences between control and TBI subjects will include means and associated 95% confidence intervals, one-way ANOVA with Scheffe post-hoc analysis, and Pearson correlation coefficients to identify possible correlations between metabolic changes and/or perfusion changes with neurological status.

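### TBI patients are scanned under continued sedation and ventilation and controls are normal volunteers, so the group contrast mixes injury with sedation/ventilation, and the plan does not say so

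*Combined protocol and SAP*

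**What the plan says.** All references are to the combined protocol and SAP.

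- **State of the patients at the scan** (TBI Patient enrollment): "Sedation and mechanical ventilation will be continued and monitored for all patients during transport and during the studies".
- **TBI group** (end of TBI Patient Exclusion Criteria): "Ten (10) severe TBI patients will have the MRS/MRI study between 3 and 7 days post-injury".
- **Controls** (Control Subject enrollment): "Five (5) age/sex matched normal volunteers will be recruited as control subjects during the first year of the study". They come from staff, students and residents. Nothing is said about sedating or ventilating them.
- **What is held the same** (Imaging Protocol Overview): "All control and TBI subjects will undergo an identical MRS/MRI protocol and neurological exam".
- **What is to be learned**: Study Objectives aims "to identify specific metabolic alterations following TBI". The Hypothesis reads "We hypothesize that following TBI, metabolic pathways are altered causing an incomplete oxidative of glucose in neurons and astrocytes".
- **Analysis** (Statistical Analysis): "Descriptive statistics used to detect statistically significant differences between control and TBI subjects" are group means with 95% confidence intervals and one-way ANOVA with Scheffe comparisons. Pearson correlations relate metabolic and perfusion changes to neurological status. No covariate, stratum or sensitivity analysis for sedation is named.
- **Data available** (Clinical Chart Review): "medication regimen, and duration of stay in the ICU will be recorded", as will the duration of ventilatory support. Neither has a role in the analysis.
- **Timing of the examination** (Neurological Assessment): day of admission and day of the MRS/MRI study.

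**The concern.** The two groups differ in at least two respects at the moment of measurement: one has a severe brain injury, and the same one is under sedation and mechanical ventilation. The outcomes are cerebral metabolism and perfusion. If sedation or ventilation moves either, the movement appears in the TBI-control difference and will be read as an altered pathway after injury. It could also run the other way and hide an injury effect.

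The protocol gives its own reasons to take this seriously. The Background ties post-traumatic hypometabolism to level of consciousness, which sedation alters. The inclusion criteria take the qualifying GCS before sedatives or paralytics are given, so the authors recognise that these drugs affect neurological status. The plan also deals explicitly with other nuisance sources, namely peripheral metabolism of the labelled substrates and tissue composition of the voxel. Sedation gets no such treatment.

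A second analysis is exposed. Depth of sedation on the scan day could influence both the metabolic measurement and the neurological findings recorded that day, and so produce a correlation between them without any link through injury.

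At stake is the first objective: a difference found by this plan could not be assigned to injury alone.

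**Working it through.** The plan states no power, alpha, SD or effect size, so it has no figure to reproduce. The checks below concern what the contrast can identify.

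**1. What the contrast estimates.** Let δ be the injury effect, s the sedation/ventilation effect, and p the fraction of TBI patients sedated and ventilated at the scan. Take controls as unsedated and the effects as additive. Then

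E(TBI mean − control mean) = δ + p·s.

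- Read literally, p = 1 and the contrast is δ + s. A linear model with an intercept, a TBI indicator and a sedation indicator has two identical columns, so its design matrix has rank 2 where 3 is needed. No covariate adjustment of the 10 v 5 comparison can separate δ from s.
- If only some patients are sedated, say p = 0.8 (assumed), the contrast is δ + 0.8·s. The model then has full rank, but δ rests on 2 unsedated patients against 5 controls. Its standard error is SD × √(1/2 + 1/5) = 0.84 SD, against SD × √(1/10 + 1/5) = 0.55 SD for the full contrast. Those two patients may also be the less severely injured.

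**2. Illustrative size.** Inputs: n = 10 and 5 (documents); two-sided alpha 0.05, equal SDs, δ = 0, p = 1 and the shift s (all assumed). SE = √0.3 = 0.548 SD, df = 10 + 5 − 2 = 13, critical t = 2.160, noncentrality = s / 0.548.

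| Assumed shift s (SD) | Noncentrality | Chance of a significant TBI-control difference |
|---|---|---|
| 0.5 | 0.91 | 14% |
| 1.0 | 1.83 | 39% |
| 1.5 | 2.74 | 72% |

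These figures would apply to any factor tied to group at 10 v 5. They show sensitivity and are not an estimate for this trial. A larger sample would not remove the bias; it would make a false attribution more likely.

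**3. Whether a dose analysis within the TBI group can rescue the claim.** With n = 10, the 5% critical correlation is t / √(t² + 8) with t = 2.306, that is 2.306 / √(5.318 + 8) = 0.63. By simulation, assuming bivariate normal data, a true correlation of 0.3, 0.5 or 0.7 is detected about 13%, 33% or 68% of the time. A correlation of 0.5 would therefore be missed about two times in three. If all ten patients received a similar dose, there would be no trend to see while the group contrast remained fully confounded.

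**The case against.** The case on the other side has five parts.

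- **The enrollment sentence may not mean that every patient is sedated.** It concerns transport and monitoring, and can mean that those already sedated stay so. The same section allows the candidate to be interviewed, and Table 2 includes sensory function and gait. This stands: the documents do not establish that all ten are sedated. It reduces complete aliasing to strong confounding and does not remove the problem.
- **A reader might infer that the sentence on an identical protocol is false.** It is not. It covers the MRS/MRI protocol and the neurological examination, makes no claim about sedation, and needs no correction.
- **The analysis is descriptive.** Statistical Analysis puts the emphasis on descriptive and graphical methods and only names the groups. That is fair as to wording. But the same section seeks statistically significant differences, and the Hypothesis is causal.
- **Some protection exists.** Medication regimen is recorded, voxel perfusion is compared with Glu and Gln enrichment, and pathway-specific labelling patterns may say more than an overall fall in flux. This limits how far one can say the objective goes unanswered. None of it separates sedation from injury in the group contrast.
- **The size is unknown.** This stands. The percentages follow wholly from the assumed shifts.

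**Conclusion.** The point holds. As planned, the TBI-control comparison estimates the joint effect of injury and sedation/ventilation, while the objectives and hypothesis assign it to TBI. The same-day correlation with neurological status is open to the same ambiguity. This rests on two readings: that most or all patients are sedated and ventilated at the scan, and that controls are not, since no such care is described for them.

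The bias cannot be sized from the documents. The figures of 14%, 39% and 72% illustrate shifts of 0.5, 1.0 and 1.5 SD with no injury effect.

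Two stronger readings are tempting and unsupported. One is that sedation explains whatever difference is found; the documents give neither size nor direction for its effect. The other is that an injury effect could be claimed if outcomes show no relation to sedative exposure among the patients. With ten patients, absence of a trend is weak evidence, dose may follow injury severity, and uniform dosing would hide the confounding altogether.

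**What to change.** - **Clinical Chart Review:** add sedative agent, dose and ventilation status at the time of the scan. Capture these prospectively, since a general medication entry may not allow infusion rates during the scan to be recovered.
- **Statistical Analysis, display:** show each metabolic and perfusion outcome in the TBI patients by sedative exposure, beside the control values. Label this as descriptive only. State that dose may follow injury severity, and that absence of a trend in 10 patients does not establish an injury effect.
- **Statistical Analysis, claim:** define the group contrast as severe TBI under ICU sedation/ventilation versus normal volunteers, and limit the conclusion to that, without attributing the difference to injury alone. Name sedation/ventilation as a limitation of this contrast and of the correlations with same-day neurological status.

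The cost is a few chart fields, some added SAP wording and a more modest claim. No change to clinical sedation is proposed.

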#### *TBI Patient Inclusion Criteria:*

- Patients will be at least 18 years of age without gender or ethnic restrictions.
- Severe accidental TBI defined as the lowest post-resuscitation GCS  $\leq 8$  prior to administration of sedatives or paralytics.
- Eligibility for MRI per routine screening checklist.

#### *TBI Patient Exclusion Criteria:*

- History of neurosurgical intervention, excluding the placement of ventriculostomy shunt
- History of a prior known brain injury with associated loss of consciousness.
- History of a known neurological disorder prior to qualifying injury.
- History of psychiatric disorder.
- History of diabetes or current unstable serum glucose level.
- Renal insufficiency or known history of kidney disease.
- Known contraindication to MRI such as, pacemaker, pregnancy, and/or other non-MR compatible implanted device.

Ten (10) severe TBI patients will have the MRS/MRI study between 3 and 7 days post-injury to target the hypometabolic period.

#### Control Subject enrollment

Five (5) age/sex matched normal volunteers will be recruited as control subjects during the first year of the study. Control subjects will be recruited from Loma Linda University and/or Medical Center

staff, student or Resident populations. The specific inclusion and exclusion criteria for the control subjects are:

*Control Subject Inclusion Criteria:*

- At least 18 years of age without gender or ethnic restrictions.
- Eligibility for MRI per routine screening checklist.

*Control Subject Exclusion Criteria:*

- MRI Department staff or subordinate of project Investigator.
- History of neurosurgical intervention, excluding the placement of ventriculostomy shunt.
- History of a prior known brain injury with associated loss of consciousness.
- History of a known neurological disorder.
- History of psychiatric disorder.
- History of diabetes or current unstable serum glucose level.
- Renal insufficiency or known history of kidney disease.
- Previous allergic reaction to gadolinium MR contrast.
- Known contraindication to MRI such as, pacemaker, pregnancy, and/or other non-MR compatible implanted device.

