#### **DSC-Perfusion Weighted imaging**

A 2D single shot gradient echo echo-planar imaging (EPI) sequence will be used to obtain DSC\_PWI using the following parameters: TR/TE = 1700/40 ms, FA = 90°, slice thickness = 5mm, matrix size = 128, and 50 measures. Gadolinium-DPTA (Gd-DTPA) contrast (0.1 mmol/kg) will be administered intravenously at the completion of the 5th scan. The resultant images are transferred to an offline program where CBV, CBF and MTT maps will be generated for each slice. To calculate CMRO2, an arterial input function is chosen from the M1 section of the middle cerebral artery for each subject. A least squares exponential fitting is used to minimize secondary circulation; a singular value decomposition deconvolution is then used to obtain estimates of CBF and CBV.

To determine the effect of substrate limitation on glucose metabolism the position of the MRS voxel will be overlaid on CBF, CBV, and CMRO2 maps using an automatic image overlay program developed in our laboratory incorporating routines from MATLAB (Version 7.0.4, MathWorks, Natick, MA, USA). The relative CBF (ml/100g/min), CBV (ml/100g), and CMRO2 (ml/100g/min) within the region of the MRS voxel will then be compared to the final C Glu and Gln enrichment pools to determine if substrate limitation correlates with metabolite enrichment.

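### Patients with TBI are not screened for a previous gadolinium reaction, although controls are and both groups receive the same contrast injection

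*Combined protocol and SAP*

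**What the plan says.** Under Imaging Protocol Overview, the protocol states: "All control and TBI subjects will undergo an identical MRS/MRI protocol and neurological exam". The section DSC-Perfusion Weighted imaging gives the contrast step: Gd-DTPA "contrast (0.1 mmol/kg) will be administered intravenously at the completion of the" fifth scan, with no distinction between patients and controls. The injection serves the study's own perfusion measurement.

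The control exclusion criteria, under Control Subject enrollment, include "Previous allergic reaction to gadolinium MR contrast". The TBI exclusion criteria do not. Their last two items are "Renal insufficiency or known history of kidney disease" and "Known contraindication to MRI such as, pacemaker, pregnancy, and/or other non-MR compatible implanted device", and nothing in the list mentions contrast.

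Three other provisions bear on whether a TBI patient is scanned:

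- The TBI inclusion criteria require "Eligibility for MRI per routine screening checklist".
- TBI Patient enrollment says "TBI participants will undergo the studies depending on clinical status as determined by the intensivist", or by the attending neurosurgeon or neurologist.
- The same section says that a member of the study team "will interview the candidate and/or family members, screen for inclusion/exclusion criteria" before obtaining consent.

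**The concern.** The protocol treats an earlier gadolinium reaction as a reason to keep a healthy volunteer out of the study. It does not say the same for a patient with severe TBI who is to receive the same agent at the same dose for the same research purpose. No reason for the difference is stated.

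The omission falls on the group less able to make up for it. A volunteer can report a past reaction. TBI patients qualify with a lowest post-resuscitation GCS of 8 or below, and sedation and ventilation continue during the studies, so many may be unable to give a history. An interview with the family is planned, but it screens against the written criteria, and those contain no item that would prompt the question.

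At stake is the avoidable exposure of a known reactor to a research injection. Re-exposure does not always cause a reaction, so the harm is possible and not certain. No endpoint, group comparison or analysis depends on this point.

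**Working it through.** The protocol gives no figure to reproduce here. The check is a comparison of the two exclusion lists, followed by a simple calculation of scale.

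**Step 1: compare the lists.** The items are paraphrased.

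| Exclusion | TBI list | Control list |
|---|---|---|
| Neurosurgical history (shunt placement allowed) | yes | yes |
| Earlier brain injury with loss of consciousness | yes | yes |
| Neurological disorder | yes (before the qualifying injury) | yes |
| Psychiatric disorder | yes | yes |
| Diabetes or unstable glucose | yes | yes |
| Renal insufficiency or kidney disease | yes | yes |
| MRI contraindication | yes | yes |
| MRI staff or investigator's subordinate | no | yes |
| Earlier gadolinium reaction | **no** | **yes** |
| Total | 7 | 9 |

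All 7 TBI items have a control counterpart, which leaves 9 − 7 = 2 items that apply to controls only. The staff item concerns recruitment and has an evident reason to be there, because controls are drawn from the institution's staff, students and residents. The gadolinium item is the only clinical exclusion without a TBI counterpart.

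**Step 2: confirm that exposure is the same.** The imaging protocol is identical for both groups, and the contrast step makes no distinction by group. All 10 + 5 = 15 planned subjects are therefore due to receive the injection.

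**Step 3: ask whether another provision covers the gap.**

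- *MRI checklist.* Its content is not in the documents, so it may or may not ask about contrast reactions.
- *MRI contraindication item.* It is open-ended, but its examples are a pacemaker, pregnancy and implanted devices. None concerns contrast.
- *Clinician's decision.* It is tied to clinical status; allergy history is not mentioned.

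The control criteria carry the checklist requirement and the contraindication item in the same words as the TBI criteria, and still name gadolinium reaction separately. The protocol's own drafting therefore does not treat those two items as sufficient.

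**Step 4: scale.** The number of TBI patients is n = 10 (stated at the end of the TBI exclusion criteria). The proportion p of TBI candidates with a known earlier reaction is not in the documents; I assume 0.1% to 1%.

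- Expected number = n × p: 10 × 0.001 = 0.01, and 10 × 0.01 = 0.1.
- Chance of at least one = 1 − (1 − p)^n: 1 − 0.999^10 = 0.00996, about 1.0%; and 1 − 0.99^10 = 0.0956, about 9.6%.

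These figures count patients with a known reaction before any other safeguard acts. They are not rates of reaction on re-exposure.

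**The case against.** The strongest reply is that the gap may exist only on paper. Every TBI patient must pass the routine MRI checklist. If that checklist asks about contrast reactions, a known reactor is already identified. The contraindication item is open-ended and could be read to include a reaction to the contrast used in this very scan. TBI patients are inpatients under a critical-care team, only hemodynamically stable ones are targeted, and Clinical Chart Review takes medical history from a record where an allergy might appear. Controls come with no treating team or admission chart described, so one can see why a written item might be thought more necessary for them. The assumed rates are also not from the documents, and actual harm would require both a failure of the other safeguards and a recurrence on re-exposure.

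Much of this stands. The documents cannot show that a known reactor would be injected, the probability is low, and the analysis is untouched. But the reply does not remove the inconsistency. The checklist and the contraindication item apply equally to controls, for whom a separate gadolinium item was still written. Chart review is described as data recording, and no written TBI criterion would make an allergy found there a reason to exclude. The idea that inpatients need the item less is inference, because the protocol gives no reason for the difference.

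**Conclusion.** The concern holds. The TBI criteria lack a safety exclusion that the protocol applies to controls, although both groups receive the same research injection. The textual difference is certain. Its practical consequence is less so, because it depends partly on a checklist that is not in the documents.

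Few, if any, of the 10 patients would be affected: 0.01 to 0.1 expected, with a chance of at least one of about 1.0% to 9.6%, if 0.1% to 1% of candidates have a known reaction. The correction should be made because it concerns participant safety, the sponsor already regards this history as a reason to exclude, and it costs very little. The point has no bearing on the study's scientific conclusions.

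**What to change.** Add "Previous allergic reaction to gadolinium MR contrast" to the TBI exclusion criteria, in the same words as for controls, and have it checked at the interview with the candidate or family already planned under TBI Patient enrollment.

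The cost is one line in the protocol and one question at that interview. The only downside is the possible loss of a rare otherwise eligible patient, 0.01 to 0.1 of 10 in expectation under the same assumption.
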